6.5 POOLING OF CENTRES

This section is not applicable because the study was performed in only two centres.

6.6 HANDLING OF MISSING DATA AND OUTLIERS

6.6.1 AE dates and times

It is not planned to impute missing values, with exception of missing AE start dates and times. These are imputed according to BI standards (see DM&SM “Handling of missing and incomplete AE dates”) [\(3\)](#)

6.6.2 Missing plasma concentrations and pharmacokinetic parameters

Handling of missing PK data will be performed according to the BI standard procedure “Noncompartmental Pharmacokinetic / Pharmacodynamic Analyses of Clinical Studies” [001-MCS-36-472_RD-01] [\(4\)](#) and [001-MCS-36-472] [\(6\)](#).

Plasma concentration-time profiles and descriptive statistics of concentration data

CTP: *Drug concentration data identified with NOS (no sample available), NOR (no valid result), NOA (not analyzed), BLQ (below the lower limit of quantification), or NOP (no peak detectable) will be displayed as such and not replaced by zero at any time point (this rule also applies also to the lag phase, including the predose values).*

Pharmacokinetic parameters and their descriptive statistics

CTP: In the non-compartmental analysis, concentration data identified with NOS, NOR, and NOA will not be considered. BLQ and NOP values in the lag phase will be set to zero. The lag phase is defined as the period between time zero and the first time point with a concentration above the quantification limit. All other BLQ/NOP values of the profile will be ignored.

6.6.3 ECG

If replicate ECG recordings are missing, the arithmetic means per time point will be computed with the reduced (1 or 2) number of recordings. If single cardiac cycles (also denoted as beats or waveforms) are missing, the arithmetic means per single ECG will be computed with the reduced (1, 2 or 3) number of cardiac cycles. If individual baseline values (i.e. pre-infusion ECGs) of all treatment cycles are missing, the combined baseline will be imputed by the screening value, while the individual baseline will be considered missing. If the screening value is missing, both baselines will be considered missing. The combined baseline will be computed as the mean of all available individual baselines over all treatment cycles. In all cases where the recording time of the planned pre-infusion ECG is after the start of infusion, change from individual baseline will be set to missing and the mistimed pre-infusion ECG will be flagged in the listing displaying the individual baseline values. The combined baseline will be computed without mistimed individual baselines. If individual baselines of all infusions/courses are mistimed, the combined baseline will be imputed by the screening value (in accordance with the rules above).

6.7 BASELINE, TIME WINDOWS AND CALCULATED VISITS

The baseline for cycle 1 analyses is the last measurement before the first drug intake in first period; The baseline for cycle 2 analyses is the last measurement before the first drug intake in the second period. The baseline for the mono-therapy is the last measurement before the first drug intake in the second peirod.

ECG

1. Individual baseline of ECG is defined as the mean of the triplicate at the time point closest to but prior to the start of infusion for each administration of volasertib.
2. Combined baseline of ECG is defined as the mean of all individual baselines of ECG across the volasertib administrations.

CTP: *For planned individual plasma concentration sampling times refer to the CTP Flow Chart. While these nominal times should be adhered to as closely as possible, the actual sampling times will be recorded and used for determination of pharmacokinetic parameter.*

Adherence to time windows will be checked via consistency check listings at the RPM/DBLM. The PK measure at 1 hour 45 mins after Volasertib infusion starts will be checked to make sure if it is measured before stop of the infusion.

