Statistical methods:	AUC _{0-tz} and C _{max} will be log-transformed prior to fitting an ANOVA model. This model will include effects for "treatment" and "subjects". 90% confidence intervals will be computed for the primary endpoints, then back-transformed to the original scale to give the point estimator and interval estimates for the geometric mean ratio (Test / Reference). Descriptive statistics for all other parameters and endpoints will be calculated.				

Proprietary confidential information.

© 2017 Boehringer Ingelheim International GmbH or one or more of its affiliated companies. All rights reserved.
This document may not - in full or in part - be passed on, reproduced, published or otherwise used without prior written permission.

FLOW CHART

OVERALL DESIGN

Proprietary confidential information.

© 2017 Boehringer Ingelheim International GmbH or one or more of its affiliated companies. All rights reserved.
This document may not - in full or in part - be passed on, reproduced, published or otherwise used without prior written permission.

TREATMENT CYCLE 1 (volasertib with itraconazole)

Visit	Day #	Planned Time [h:min]	Approximate clock time of actual day [h:min]	Event and comment	Safety Laboratory ² (S), Coagulation (C)	PK _{plasma} volasertib + CD 10899, itraconazole	Vital signs (BP and PR), ECG (digital, triplicate)	Adverse events/ Con. med
SCREEN	-14 to -4			screening ¹ , ECOG blood samples for additional screening lab parameters	S ² , C		X	
1	-4	-88:00	16:00	admission to trial site ³ review of in-and exclusion criteria				
	-3	-72:00	8:00	itraconazole 200 mg				
	-2	-48:00	8:00	itraconazole 200 mg				
	-1	-24:00	8:00	itraconazole 200 mg		X ^{10, 12}		
	1	-0:30	7:30	blood samples for pharmacogenomics ⁹	S	X	X	
	1	-0:05	7:55	itraconazole 200 mg				
		0:00	8:00	start of iv volasertib infusion, ECOG				
		0:30	8:30				X ⁴	
		1:00	9:00			X	X ⁴	
		1:45 ⁷	9:45	physical examination		X	X	
1		2:00	10:00	end of iv volasertib infusion, ECOG				
		3:00	11:00				X	
		4:00	12:00			X		
		6:00	14:00			X ¹¹	X ⁶	
		8:00	16:00			X ¹¹		
		12:00	20:00			X		
	2	24:00	8:00	itraconazole 200 mg	C	X ¹²	X ⁶	
		36:00	20:00			X ¹¹		
	3	48:00	8:00	itraconazole 200 mg		X ¹²		
	4	72:00	8:00	itraconazole 200 mg discharge from trial centre subjects will continue to take itraconazole 200 mg once daily until Day 15 and would receive a diary card to note down the date and time of itraconazole intake at home		X ^{11, 12}		
2	8	168:00	8:00	itraconazole 200 mg	S	X ^{11, 12}	X ⁴	

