9. Can be taken also at any later time point from those patients who received at least first cycle of volasertib.
10. Analysed for itraconazole only
11. Analysed for volasertib and CD 10899 metabolite only
12. PK sampling should be taken just before itraconazole intake

Proprietary confidential information.

© 2017 Boehringer Ingelheim International GmbH or one or more of its affiliated companies. All rights reserved.
This document may not - in full or in part - be passed on, reproduced, published or otherwise used without prior written permission.

TREATMENT CYCLE 2 (volasertib without itraconazole)

Visit	Day	Planned Time [h:min]	Approximate clock time of actual day [h:min]	Event and comment	Safety Laboratory (S), Coagulation (C)	PK _{plasma} volasertib and CD 10899	Vital signs (BP and PR), ECG (digital, triplicate)	Adverse events/ Con. med
1	-1	-17:00	15:00	admission to trial site ^{1,2}				
	1	-0:30 ⁶	7:30	review of in-and exclusion criteria	S	X	X	
		0:00	8:00	start of iv volasertib infusion, ECOG ▲				
		0:30	8:30				X ³	
		1:00	9:00			X	X ³	
		1:45 ⁸	9:45	physical examination		X	X	
		2:00	10:00	▼ end of iv volasertib infusion, ECOG				
		3:00	11:00				X	
		4:00	12:00			X		
		6:00	14:00			X	X ⁷	
		8:00	16:00			X		
		12:00	20:00			X		
	2	24:00	8:00		C	X	X ⁷	
		36:00	20:00			X		
		48:00	8:00			X		
2	8	168:00	8:00	discharge from trial centre		S	X	X ³
3	15	336:00	8:00				X	
4 ⁹	22	504:00	8:00	physical examination, body weight, ECOG, tumour assessment, eligibility for further treatment cycle ⁴	S, C	X	X ³	

1. Patients should be admitted to hospital and stay until day 4 (72h after start of infusion)
2. Pregnancy test in women of childbearing potential
3. Vital signs only
4. Only patients with clinical benefit after volasertib treatment based on investigator's assessment (clinical response, or absence of progression, or symptom improvement) will qualify for further participation in the trial. In case of symptom improvement despite disease progression a repeated cycle may be allowed upon the agreement of the clinical monitor and the investigator.
5. Safety lab includes haematology, and serum biochemistry. For detail see [5.2.3](#). Urinalysis (dipstick) is only performed at screening and EOT.
6. For predose sampling of volasertib and CD 10899 in plasma, metabolic profiling, the time window is 2 hours before start of infusion.
7. ECG only
8. Shortly before end of infusion
9. This visit may co-incide with visit 1 of treatment cycle 3

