6. GENERAL ANALYSIS DEFINITIONS

6.1 TREATMENTS

In total, it was planned to include 24 patients in this two period trial with a fixed treatment sequence:

Treatment A: Day -3 to Day 15 of cycle 1: daily 200mg itraconazole

Day 1 of cycle 1: Single dose volasertib infusion 300mg

Treatment B: Day 1 of cycle 2 (Day 23 starting from Day 1 of cycle 1): Single dose volasertib infusion 300mg

For detail of dosage and formulation see section 4.1 in CTP. For detailed information on the handling of the treatment in the O*C views refer to Technical TSAP ADS plan

Time intervals for safety analysis are defined below. The analyses for safety endpoints will focus the on-treatment period of volasertib and contrast the safety profile within first cycle and second cycle during the study period. In addition, the safety endpoints will be summarized for the entire volasertib mono-therapy period.

Screening period: Screening to first dose of Itraconazole.

Itraconazole induction period: Start of first dose of Itraconazole to start of first dose of volasertib.

First cycle combo-therapy period: Start of first dose of volasertib to the start of the second cycle if patients received the second cycle mono-therapy, or to the 21 days after the first volasertib administration date if patients discontinued after the first cycle.

Second cycle mono-therapy period: Start of second dose of volasertib to the start of the cycle 3 if patients received cycle 3 mono therapy, or to the 21 days after second volasertib administration date if patients discontinued after the second cycle.

Mono-therapy period: Start of the second dose of volasertib to the last dose of volasertib plus 21 days.

Post-treatment period: After 21 days after last dose of volasertib.

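### Does the cycle 1 safety baseline in SAP 6.7 have to name the drug that anchors it?

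*SAP*

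**What the plan says.** SAP 6.7 gives the general rule: "The baseline for cycle 1 analyses is the last measurement before the first drug intake in first period". Cycle 2 and the mono-therapy period get the same form of words, referring to the second period. The ECG rule in the same section is more specific. It takes the triplicate closest to, but "prior to the start of infusion for each administration of volasertib".

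SAP 6.1 can be read two ways on what the first period is. It opens with "In total, it was planned to include 24 patients in this two period trial with a fixed treatment sequence", and the first treatment begins with itraconazole: "Treatment A: Day -3 to Day 15 of cycle 1: daily 200mg itraconazole". It then defines the safety intervals, where the lead-in is a period of its own and the next one is "First cycle combo-therapy period: Start of first dose of volasertib to the start of the second cycle". The same section says the safety analyses concentrate on the volasertib on-treatment period.

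The baseline is used in SAP 7.8.2 (change from baseline and CTCAE transitions for the primary laboratory tests) and SAP 7.8.4 (changes in blood pressure and pulse rate). Protocol 7.3.3 adds a descriptive comparison of cycle 1 with cycle 2 and mentions change from screening and/or baseline.

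**The concern.** Read literally, the first drug taken in cycle 1 is itraconazole on day -3, which makes screening the baseline. Read through the SAP's own safety periods, it is volasertib on day 1. Two programmers could each claim to follow the SAP and produce different cycle 1 tables.

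The choice carries meaning. Measured from screening, the cycle 1 change includes the itraconazole lead-in and the days since screening. Measured from day 1, any lead-in effect sits inside the baseline and is not counted. The cycle 2 baseline is the same either way, so the difference passes into the comparison of combination with volasertib alone. In an open-label trial one would like that choice fixed before the data are seen. The ECG rule shows that tighter wording was available.

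**Working it through.** **Do two candidate values exist?** The inputs are the protocol flow charts for cycles 1 and 2 and protocol 5.2.3, 5.2.5.1 and 6.2.1. Times are counted from the start of volasertib, with no day 0.

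- Screening row, day -14 to -4 (the row with "blood samples for additional screening lab parameters"): safety laboratory, coagulation, vital signs and ECG.
- Itraconazole at -72, -48 and -24 h: 3 × 200 mg = 600 mg.
- Day 1, -0:30 (the row with "blood samples for pharmacogenomics"): safety laboratory, vital signs and ECG, but no coagulation sample.
- Cycle 2 day 1, -0:30 (the row with "review of in-and exclusion criteria"): safety laboratory, vital signs and ECG.

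| Parameter | Last value before itraconazole | Last value before volasertib | Differ? |
|---|---|---|---|
| Haematology, biochemistry | screening | day 1, -0:30 | yes |
| Vital signs | screening | day 1, -0:30 | yes |
| Coagulation | screening | screening | no |
| ECG change from individual baseline | rule names the infusion | day 1, -0:30 | no |
| Cycle 2, laboratory and vital signs | not applicable | cycle 2 day 1, -0:30 | no |

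**How far apart are they?** Day -14 is -336 h and day -4 is -96 h. Then (336 - 0.5)/24 = 13.98 days and (96 - 0.5)/24 = 3.98 days, so about 4 to 14 days. Protocol 6.2.1 accepts a laboratory result from up to 14 days before the screening visit, which gives at most 14 + 14 = 28 days. Protocol 5.2.3 lets the day 1 laboratory sample be drawn up to 2 days early, at -48 h. That is still after the -72 h dose, so the two values remain distinct.

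**What does the choice do to the tables?** Let d be the day 1 value minus the screening value. For one patient, change from screening = change from day 1 + d, and mean changes move by the mean of d. Medians and CTCAE transitions do not move by a fixed amount.

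The documents give no value for d. As an assumed illustration, take ALT in multiples of the upper limit of normal, 1.0 at screening with a worst value of 2.5. The change from screening is 2.5 - 1.0 = 1.5. The change from day 1 is 2.5 - (1.0 + d), which is 1.5, 1.25, 1.0 and 0.5 for d = 0, 0.25, 0.5 and 1.0. Nothing in the documents supports a shift at the upper end after three doses, so this shows the arithmetic and not a size.

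If the lead-in has no effect, d is noise. With within-patient standard deviation s and independent occasions, the standard error of the mean of d is s × √(2/n). For n = 24 it is 0.289 s, and 1.96 × 0.289 s = 0.57 s. However, 24 is the target for evaluable patients who complete both cycles. SAP 7.4 reports that two of the first three stopped after cycle 1, and such patients are replaced. If the target was met, at least 26 patients had a cycle 1, and the figure is 1.96 × √(2/26) s = 0.54 s. This is extra scatter around the same expected value, not bias.

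**Which reading do the documents favour?**

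- SAP 6.7 pairs cycle 1 with the first period and cycle 2 with the second. The named safety intervals in SAP 6.1 pair in the same way, and the first-cycle interval begins at volasertib.
- SAP 6.1 gives the itraconazole lead-in its own interval, outside that period.
- Protocol 7.3.3 treats screening and baseline as separate references. If baseline meant the last value before itraconazole, the two would coincide for these parameters.
- Protocol 5.2.4 explains baseline as the value before the current infusion, though only for QTcF.

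All four point to day 1.

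**The case for a change.** The best case for a change is that it would be cheap and the effect is not confined to a few patients. One phrase in SAP 6.7 would close the question, both values are already scheduled, and every patient with a cycle 1 is touched. The literal wording does favour itraconazole, and SAP 6.7 never links its first period to the safety intervals of SAP 6.1. That much stands: the sentence is incomplete, and naming the drug would be tidier.

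The rest is weaker. Neither baseline is wrong. An untreated screening value captures the whole effect of the combination regimen; a day 1 value is closer in time and matches the ECG rule. Preferring one is a trade-off. Nor does day 1 make the comparison of cycles clean, because the cycle 2 baseline follows a full combination cycle with itraconazole up to day 15. A missing day 1 value is already handled, since a last-measurement rule falls back to the previous one. The claim that the choice would be made after seeing the data is not established: the plan relies on a company guideline on laboratory data and a technical analysis plan, neither of which is available here. SAP section 7 also lists individual values by visit, so both candidates remain visible.

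A related worry is that protocol 7.3.3 defines the safety population by study drug, without saying which. It has no shown consequence. SAP 6.3 and 7.8 name volasertib explicitly, and SAP 7.8.1 lists adverse events from the lead-in.

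**Conclusion.** No change to the plan follows. SAP 6.7 leaves out a detail that analysts would fill sensibly from SAP 6.1, most naturally with the last value before the first volasertib infusion. No stated rule produces a wrong result, and the other reading also gives defensible descriptive tables.

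The reach is limited to the cycle 1 change tables for haematology, biochemistry and vital signs, the CTCAE shifts, and the descriptive comparison between cycles. The trial tests no confirmatory hypothesis (protocol 7.2), and its primary pharmacokinetic analysis is untouched.

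This conclusion assumes that one baseline is applied consistently across the cycle 1 tables and that any lead-in shift over three itraconazole doses is modest. The documents neither support nor exclude a larger shift; if one occurred, the visit listings would show it.

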7. PLANNED ANALYSIS

The format of the listings and tables will follow the standards defined in the BI corporate guideline “Reporting of clinical trials and project summaries” [\(5\)](#).

The individual values of all subjects will be listed, sorted by treatment sequence, subject number and visit. The listings will be included in Appendix 16.2 (SDL) of the CTR.

The following standard descriptive statistical parameters will be displayed in summary tables of continuous variables for non-PK parameters.

N	number of non-missing observations
Mean	arithmetic mean
SD	standard deviation
Min	minimum
Median	median
Max	maximum

Tabulations of frequencies for categorical data will include all possible categories and will display the number of observations in a category, as well as the percentage (%) for each treatment. Percentages will be rounded to one decimal place. The category ‘missing’ will be displayed only if there are actual missing values. Percentages will be based on all subjects in each subject set.

Units of variables should be given in the titles or column/row descriptors in square brackets (e.g. [mg]).

CTP: *The following descriptive statistics will be calculated for plasma concentrations as well as for all primary and secondary PK parameters: N, arithmetic mean, standard deviation, minimum, median, maximum, arithmetic coefficient of variation, geometric mean, and geometric coefficient of variation. The data format for descriptive statistics of concentrations will be identical with the data format of the respective concentrations. The descriptive statistics of PK parameters will be calculated using the individual values with the number of decimal places as provided by the evaluation program. Then the individual values as well as the descriptive statistics will be reported with 3 significant digits in the clinical trial report.*

7.1 DEMOGRAPHIC AND OTHER BASELINE CHARACTERISTICS

Only descriptive statistics are planned for this section of the report, based on TS. The following variables will be displayed: Gender, Race, Age, Baseline height, weight, body surface area, and body mass index, smoking and alcohol status, baseline ECOG

7.2 CONCOMITANT DISEASES AND MEDICATION

Frequency tables are planned for this section of the report, based on the TS.

Concomitant disease will be coded using the coding system of the Medical Dictionary for Drug Regulatory Activities (MedDRA). Concomitant medications will be coded using the World Health Organization Drug Dictionary (WHO-DD). The coding version number will be displayed as a footnote in the respective output.

The diagnoses and medications will be listed. Subjects without any concomitant diagnoses or concomitant therapies should be noted by a "No" in the respective column.

7.3 TREATMENT COMPLIANCE

It is not intended to list compliance separately. Any deviations from complete intake will be addressed in the RPM/DBLM (see [Section 6.2](#)).

7.4 PRIMARY ENDPOINTS

The relative bioavailability will be investigated based on the PK parameters AUC_{0-tz} and C_{max} for volasertib and its main metabolite CD10899, respectively.

The statistical model used for the analyses will be a repeated measure ANOVA (analysis of variance) model on the logarithmic scale and will be based on both the primary and sensitivity PKS.

CTP: *The statistical model used for the analysis of AUC_{0-tz} , C_{max} of volasertib and CD10899 will be an analysis of variance (ANOVA) model with repeated measure on the logarithmic scale. The effect 'subject' will be considered as random, whereas the effect 'treatment' will be considered as fixed. The model is described by the following equation:*

$y_{km} = \mu + \tau_k + s_m + \varepsilon_{km}$, where

y_{km} = logarithm of response (AUC_{0-tz} or C_{max}) in subject m receiving treatment k ,

μ = the overall mean,

τ_k = the k -th treatment effect, $k = 1, 2$,

s_m = the effect associated with the m -th subject, $m=1, \dots, n$,

ε_{km} = the random error associated with the m -th subject receiving treatment k .

CTP: *The PK parameters AUC_{0-tz} and C_{max} will be log-transformed (natural logarithm) prior to fitting the ANOVA model. The difference between the expected means for $\log(T)$ - $\log(R)$ will be estimated by the difference in the corresponding least square means (point estimate) and 2 sided 90% confidence intervals based on the t -distribution will be computed. These quantities will then be back-transformed to the original scale to give the point estimator*

(geometric mean) and interval estimates for the intra-subject ratio of the geometric means for treatments test and reference.

As stated in the CTP, in case the tolerable dose of volasertib is less than the initial dose level 300mg, dose would be included as a covariate in the ANOVA model. However, as a consequence of immediate dose de-escalation after first three patients treated on 300mg and two of them discontinued after cycle 1, tolerable dose was de-escalated to 250mg and all subsequently enrolled patients were treated on 250mg. Due to the limited dose levels and sparse data available on 300mg, instead of including dose as an additional covariate in the ANOVA model according to the CTP, primary analysis using ANOVA model on log transformed PK endpoints will be performed based on the clean cohort of patients who were treated on equal dose levels (either 250mg or 300mg) throughout both cycles 1 and 2. In addition, a sensitivity analysis will be performed by including the patients with further intra-individual dose reduction from 250mg to 200mg in cycle 2. In the sensitivity analysis, dose proportionality (BI 1230.5, BI 1230.23) will be applied on individuals with dose reduced to 200mg during cycle 2 volasertib mono therapy to rescale the PK measures. However, since dose proportionality was not established for the combination therapy of volasertib + itraconazole, dose normalization will not be applied on the patient who was treated on 300mg in both cycle 1 and 2.

